The tertiary objective of this study is to assess optional pharmacokinetics (PK) (ie, area under the concentration-time curve [AUC], clearance [CL], maximum plasma concentration [C_{max}], terminal elimination half-life [$t_{1/2}$], and time to maximum plasma concentration [T_{max}]) of CAMB after 5 days of oral administration.

POPULATION:

The population for this study will be women age 18 to 65 years, inclusive, with a clinical diagnosis of moderate to severe VVC.

STUDY DESIGN AND DURATION:

This is a proof-of-concept, multi-center, randomized study to evaluate the safety, tolerability, and efficacy of 200 mg (100 mg BID) CAMB and 400 mg (200 mg BID) CAMB compared with a single 150 mg dose of fluconazole in the treatment of moderate to severe VVC.

Approximately 100 women with moderate to severe VVC will be randomized in a 1:1:1 ratio to 1 of 3 treatment groups (200 mg CAMB, 400 mg CAMB, or fluconazole). Randomization will be stratified by a signs and symptoms composite score of up to 12 (moderate) and ≥ 13 (severe).

Scoring of Symptoms and Signs of Vulvovaginal Candidiasis

Vulvovaginal candidiasis signs and symptoms will be evaluated at screening and Days 1, 5, and 12. Signs of VVC will be defined as the presence of erythema, edema, or excoriation. Symptoms of VVC will be defined as itching, burning, or irritation.

Each vulvovaginal sign and symptom will be objectively scored based on severity as follows:

- 0 = none (complete absence of any signs or symptoms),
- 1 = mild (slight),
- 2 = moderate (definitely present), or
- 3 = severe (marked, intense).

Dosing Schedule

For subjects randomized to 200 mg CAMB and 400 mg CAMB, the preferred dosing regimen on Days 1 through 4 is 100 mg BID and 200 mg BID, respectively, with morning and evening meals. On Day 1, subjects will be administered the first dose according to their treatment assignment with a non-standardized meal or snack in the clinic.

On Day 1, subjects randomized to 200 mg CAMB who enroll in the afternoon can take both 100 mg doses as a single 200 mg dose or as 2 separate doses with a non-standardized meal or snack (once at enrollment and once in the evening); subjects randomized to 400 mg CAMB who enroll in the afternoon can take both 200 mg doses as a single 400 mg dose or as 2 separate doses with a non-standardized meal or snack (once at enrollment and once in the evening).

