On Day 5, subjects randomized to 200 mg CAMB and 400 mg CAMB will be administered a single dose of 200 mg and 400 mg, respectively, in the clinic with a non-standardized meal or snack.

Other combinations of CAMB dosing are allowed throughout the study such that subjects randomized to 200 mg CAMB complete a course of ten 100 mg doses by Day 5 and subjects randomized to 400 mg CAMB complete ten 200 mg doses by Day 5. Subjects will be instructed to record their dosing in a patient diary.

Subjects randomized to fluconazole will take a single 150 mg tablet on Day 1 without respect to food.

Visit Schedule

Participation in this study will consist of a screening period (up to 48 hours prior to Day 1); a 5-day treatment period (5 days with 200 mg or 400 mg CAMB or 1 day with fluconazole); a mandatory pre-dose PK assessment on Day 5 for determination of trough plasma concentrations of CAMB; an optional serial PK assessment for subjects who agree to participate; a TOC/Early Withdrawal Visit on Day 12 (± 2 days), and a follow-up phone call between Days 21 to 30. For eligible subjects, screening and Day 1 can occur on the same day. Therefore, subjects who do not participate in the optional serial PK assessment will complete a total of 3 to 4 clinic visits, and subjects who do participate will complete a total of 4 to 5 clinic visits.

At screening, subjects must provide written informed consent prior to any study procedures being performed. Papanicolaou (Pap) smear/tests will be performed for subjects (>21 years of age) who do not have a negative test for intraepithelial lesion or malignancy or atypical squamous cells of

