6. Has other urogenital infection(s) that would potentially alter their response to disease;
7. Has confirmed or suspected *N. gonorrhoea* or *C. trachomatis*;
8. Has another vaginal or vulvar condition that would confound the interpretation of clinical response;
9. Has a physiological or pathological condition that would confound the interpretation of clinical response (eg, cervicitis, aerobic vaginitis, atrophic vaginitis, and mucoid ectopy);
10. Has any of the following laboratory abnormalities at screening:
 - a. Alanine aminotransferase (ALT), or aspartate aminotransferase, or alkaline phosphatase levels $>5 \times$ upper limit of normal (ULN);
 - b. Total bilirubin level $>2.5 \times$ ULN;
 - c. Estimated creatinine clearance <70 mL/min;
 - d. Absolute neutrophil count less than 500 cells/ μ L; or
 - e. Potassium level ≤ 3.5 mmol/L;
11. Plans to undergo treatment or surgery for cervical intraepithelial neoplasia or cervical carcinoma during the study period;
12. Has any known azole-resistant *Candida* infection;
13. Has documented Type I diabetes mellitus, use of insulin, or glycosylated hemoglobin A_{1c} level $>10\%$ within 6 months of enrollment;
14. Has previously diagnosed human immunodeficiency virus seropositivity or clinically diagnosed acquired immunodeficiency syndrome or its related complex;
15. Has a known immunosuppressive condition (eg, end-stage renal disease) or is currently taking immunosuppressants, (eg, steroids, cyclosporine);
16. Is currently receiving therapy with a drug known to prolong QTc interval that is metabolized via the cytochrome P450 3A4 enzyme, such as cisapride, astemizole, pimozide, and quinidine;
17. Has been exposed to any investigational agent during the last month (30 days or 5 half-lives, whichever is longer) prior to screening; or
18. Has any other condition the Investigator believes would interfere with the subject's ability to provide informed consent, comply with study instructions, or puts the subject at undue risk.

DOSAGE FORMS AND ROUTE OF ADMINISTRATION:

Encocleated amphotericin B will be administered as a 5 mg/mL oral suspension of 200 mg (100 mg [20 mL] BID) or 400 mg (200 mg [40 mL] BID) amphotericin B on Days 1 through 5.

Fluconazole will be administered once as a single 150 mg tablet on Day 1.

ANALYSIS POPULATIONS:

The Intent-to-Treat Population (ITT) will include all subjects who were randomized.

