The Modified Intent-to-Treat (mITT) Population will include all randomized subjects who have a *Candida* species isolated on culture of vaginal specimen at baseline based on the central laboratory results.

The Safety Population will include all ITT subjects who received at least 1 dose of study drug.

The PK Population will include the subjects in the ITT Population with at least 1 PK sample.

The Per-Protocol Population will include all of the mITT subjects who meet the following criteria:

- No key inclusion/exclusion violations;
- Received the complete course of study drug;
- No major protocol violations that would affect the treatment evaluation; and
- Has not received another systemic or topical antifungal drug that has documented activity against the causative organism before the TOC assessment, unless the subject has a therapeutic response of failure at a previous assessment visit.

EFFICACY VARIABLES:

The efficacy endpoints for this study will be performed on the mITT Population and Per-Protocol Population and will include the following:

1. The proportion of subjects with clinical cure at the TOC Visit (Day 12);
2. The proportion of subjects with mycological eradication at the TOC Visit (Day 12); and
3. The proportion of subjects with overall success at the TOC Visit (Day 12).

For the definition of clinical cure, mycological eradication, and overall success, see below.

Assessment of Clinical Outcome

Clinical outcomes will be assessed at the TOC Visit (Day 12) according to the following definitions:

- Clinical cure – resolution of the VVC signs and symptoms that were present at baseline without further antifungal treatment. Specifically, any sign or symptom with a score of 1 or 2 at entry should be absent (score = 0) by the TOC Visit. Any sign or symptom with a score of 3 (severe) at entry should have a score of 0 or 1 by the TOC Visit. If a new sign or symptom is observed at the TOC Visit that was not present at entry, the Investigator should state whether the new sign or symptom is related to VVC or not (ie, if related, the subject would be considered a failure; if not related, the subject may be considered a cure);
- Clinical failure – incomplete resolution of signs and symptoms of VVC that were present at baseline or new signs and symptoms have developed and require the initiation of non-study antifungal drugs; and
- Clinical indeterminate – insufficient data are available to determine if the subject is a cure or failure.

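### The Per-Protocol completion rule removes a CAMB subject who fails early, stops and is given another antifungal, but keeps a comparable fluconazole failure (minor)

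*Combined protocol and SAP*

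**What the plan says.** The Synopsis, under Analysis Populations, forms the Per-Protocol Population from mITT subjects who meet four criteria jointly. One is "Received the complete course of study drug", with no threshold and no exception. Another bars a further antifungal active against the causative organism before Test of Cure (TOC), "unless the subject has a therapeutic response of failure at a previous assessment visit". That qualifier belongs to the antifungal criterion alone.

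The course differs by arm. Dosage Forms and Route of Administration states: "Fluconazole will be administered once as a single 150 mg tablet on Day 1". Dosing Schedule has "subjects randomized to 200 mg CAMB complete a course of ten 100 mg doses by Day 5", and ten 200 mg doses in the other CAMB arm. It adds "Other combinations of CAMB dosing are allowed throughout the study" so long as the course is finished by Day 5, so missed doses can be made up.

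On timing, "signs and symptoms will be evaluated at screening and Days 1, 5, and 12", and Visit Schedule lists "a TOC/Early Withdrawal Visit on Day 12". Subjects are also told on Day 1 to contact the investigator for reassessment if they have not improved in 2 to 3 days. The outcome categories, however, are fixed later: "Clinical outcomes will be assessed at the TOC Visit (Day 12) according to the following definitions". The mycological and overall categories are likewise defined at TOC.

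Statistical Analyses summarizes efficacy descriptively in both the mITT and Per-Protocol Populations and does not say which one leads.

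**The concern.** By writing a failure exception, the plan shows that it means to keep treatment failures in the Per-Protocol set rather than lose them because they were rescued. The completion criterion can defeat that aim, and it can do so only in the CAMB arms. The same event, early failure followed by another antifungal, would then count in the fluconazole denominator and vanish from a CAMB denominator.

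At stake is the comparability of the Per-Protocol cure, eradication and overall success rates in a proof-of-concept trial that reports them beside the mITT rates. Sampling error would show in an interval. Selective removal would not show unless exclusions are listed by arm.

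A secondary point is that the exception depends on a failure at an earlier visit, while the synopsis defines failure only at TOC. A failure can be observed earlier, since Day 5 scores exist, but no stated rule turns those scores into a failure.

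**Working it through.** **1. The plan's own figure.** Sample Size Determination plans 75 mITT subjects, with 75% of those randomized evaluable: 75 / 0.75 = 100, as stated. With 1:1:1 allocation, 75 / 3 = 25 mITT subjects per arm. The plan gives no power, effect size, cure rate or completion rate.

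**2. The same history in each arm.** Take a subject who takes the first dose, is reassessed for non-improvement at 2 to 3 days, is recorded as a failure and receives another antifungal.

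- Fluconazole: the course was complete on Day 1, so the completion criterion is met. The exception covers the antifungal criterion. She stays.
- CAMB, stopped at that point: the exception covers the antifungal criterion, but ten doses were not taken. The criteria apply jointly, so she is removed.
- CAMB, failure found on Day 5: the last dose is given in clinic that day, so she can complete the course and be treated afterwards. She stays, as on fluconazole.

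The asymmetry is real, but it arises through the reassessment at 2 to 3 days and not through the scheduled Day 5 visit.

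**3. Size, on assumed values.** Let n be mITT subjects in a CAMB arm, k the non-completers removed, p the arm's cure rate and q the cure rate among those removed. Then

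shift = (Per-Protocol rate) − p = k/(n − k) × (p − q).

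For failed non-completers q = 0. With n = 25 and an assumed p = 60% (15/25):

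- k = 1: 15/24 = 62.5%, +2.5 points
- k = 2: 15/23 = 65.2%, +5.2 points
- k = 3: 15/22 = 68.2%, +8.2 points

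A fluconazole arm at 15/25 stays at 60% under this criterion. For other assumed cure rates:

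- p = 40%: 10/24 = 41.7% (+1.7) to 10/22 = 45.5% (+5.5)
- p = 80%: 20/24 = 83.3% (+3.3) to 20/22 = 90.9% (+10.9)

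**4. Direction.** The criterion also removes CAMB subjects who stop for other reasons. If q = p the shift is zero. If all those removed were cured (q = 100%, p = 60%), 14/24 = 58.3% (−1.7) for k = 1 and 12/22 = 54.5% (−5.5) for k = 3. The documents give nothing from which to choose q.

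**5. Scale.** At 60% and 25 per arm, the 95% half-width for a difference is 1.96 × √(2 × 0.6 × 0.4 / 25) = 27.2 points. Every shift shown at 60% is smaller than that.

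**The case against.** The strongest reply is that this is what a completer set does. Any completion rule reaches more subjects on a five-day regimen than on a single tablet. The mITT analysis does not depend on completion, the sample size is set on mITT, and efficacy is secondary and descriptive, with no test or margin. Make-up dosing should keep non-completion low. The scenario needs a failure recorded and CAMB stopped mid-course, and the synopsis describes no stopping of CAMB for lack of effect. All of this stands, and it is why the point is minor. It does not answer the narrower inconsistency: the plan protects early failures in one criterion and loses them in another, in the CAMB arms only.

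Three stronger readings are tempting, and the documents do not support them.

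- A reader might infer that the Per-Protocol comparison favors CAMB. The sign depends on why subjects stop and how often they are cured, and neither is given.
- A reader might infer that CAMB failures in general are dropped. Those who complete the course, including failures first seen on Day 5, are kept.
- A reader might infer that a rescued subject is already a failure by definition. Assessment of Clinical Outcome rules out cure after further antifungal treatment, but its failure category needs incomplete resolution, or new findings that require treatment. A rescued subject whose signs and symptoms resolve is not literally assigned to it.

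The text available is the synopsis, so the lack of a pre-TOC failure criterion is shown only there.

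**Conclusion.** The point holds as a minor inconsistency in the Per-Protocol definition. After the first dose the completion criterion can exclude only CAMB subjects, and the failure exception does not cover it, so one narrow class of early CAMB failures is removed while its fluconazole counterpart stays. The reach of the rule follows from the text. The size does not: the 2.5 to 8.2 points rest on an assumed 60% cure rate, 25 subjects per arm and 1 to 3 removed subjects who all failed. The net direction across all non-completers is unknown. Safety, the primary objective, and the mITT results are untouched.

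**What to change.** Change analysis wording only, and settle it before outcomes by arm are reviewed.

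1. Attach the existing failure exception to the completion criterion as well, so that subjects with a recorded therapeutic failure before TOC stay in the Per-Protocol Population in every arm. Leave the antifungal criterion otherwise unchanged.
2. State that these subjects count as clinical and overall failures. Flag cultures taken after another antifungal in the mycology table, since they may reflect that drug.
3. For this exception, tie an earlier failure to the Day 5, unscheduled or early-withdrawal assessment.
4. Tabulate Per-Protocol exclusions by arm and reason, and read Per-Protocol as supportive of mITT.

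It would be tempting to go further and also keep everyone who stopped for lack of effect or an adverse event, with the observed outcome. I would not: subjects who stop because they feel better would still be left out, so retention would depend on outcome.

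The cost is one clause, two short definitions and one table. The set becomes less purely a completer set. The change also leaves a gap of its own: CAMB subjects who stop for other reasons, including feeling better, remain excluded, so any remaining tilt may run against CAMB. If three such subjects were all cured, 15/25 (60%) becomes 12/22 (54.5%). The exclusion table is what makes that visible.

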Assessment of Mycological Outcome

Mycological outcomes will be assessed at Day 12 (± 2 days) (TOC Visit) according to the following definitions:

- Mycological eradication – a vaginal swab culture negative for growth of baseline *Candida* species;
- Mycological persistence – a vaginal swab culture positive for growth of baseline *Candida* species; and
- Mycological indeterminate – no vaginal swab culture is available, or the culture cannot be interpreted for any reason, or the culture is considered contaminated.

Assessment of Overall Response

Overall response will be assessed at Day 12 (± 2 days) (TOC Visit) according to the following definitions:

- Overall success – achievement of both a clinical cure AND microbiologic eradication;
- Overall failure – clinical failure OR microbiological persistence; and
- Overall indeterminate – insufficient data are available to determine if the subject is an overall success or failure.

The assessment of overall response at the TOC Visit is summarized below.

Summary of Overall Response at the Test-of-Cure Visit

Clinical Outcome	Mycological Outcome		
	Eradication	Persistence	Indeterminate
Cure	Success	Failure	Indeterminate
Failure	Failure	Failure	Failure
Indeterminate	Indeterminate	Failure	Indeterminate

SAFETY VARIABLES:

Safety assessments will include clinical laboratory assessments (including serum chemistry, hematology, and urinalysis), vital signs, body weight, ECGs, both complete and symptom-based physical examinations, prior and concomitant medication reporting, and adverse event reporting.

Hepatotoxicity

Hepatotoxicity will be defined as post-baseline aminotransferase $\geq 3 \times$ ULN.

Nephrotoxicity

Nephrotoxicity will be defined as a 50% increase in serum creatinine from baseline or an increase by ≥ 0.3 mg/dL.

Hypokalemia

Hypokalemia will be defined as serum potassium ≤ 2.5 mmol/L.

PHARMACOKINETIC PARAMETERS:

The PK parameters will include the following:

- AUC: area under the concentration-time curve,
- CL: clearance,
- C_{\max} : maximum plasma concentration,
- C_{trough} : concentration of pre-dose CAMB,
- $t_{1/2}$: terminal elimination half-life, and
- T_{\max} : time to maximum plasma concentration.

STATISTICAL ANALYSES:

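### Mycological eradication is judged on the test-of-cure culture alone, so clearance after a non-study antifungal is credited to the randomized drug in endpoint 2

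*Combined protocol and SAP*

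**What the plan says.** All references are to the Synopsis of the combined protocol and SAP.

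- **Assessment of Clinical Outcome.** Cure is "resolution of the VVC signs and symptoms that were present at baseline without further antifungal treatment". The bar covers any further antifungal, whatever the reason for giving it.
- **Assessment of Mycological Outcome.** Eradication is "a vaginal swab culture negative for growth of baseline" Candida species. Persistence is the same test with a positive result. Indeterminate covers a missing or contaminated culture, or one where "the culture cannot be interpreted for any reason". None of the three mentions other antifungals.
- **Assessment of Overall Response.** Success needs both clinical cure and eradication.
- **Efficacy Variables.** The proportion with eradication at TOC is endpoint 2, listed separately from clinical cure (1) and overall success (3), for the mITT and Per-Protocol Populations.
- **Analysis Populations.** The Per-Protocol set leaves out subjects given another active antifungal before TOC. It makes one exception, for earlier failures; the criterion applies "unless the subject has a therapeutic response of failure at a previous assessment visit".
- **Objectives and Statistical Analyses.** Comparing the eradication rates of CAMB and fluconazole is a secondary objective. The efficacy analysis is descriptive.

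**The concern.** The plan treats another antifungal before TOC as disqualifying for clinical cure and, through cure, for overall success. It also restricts such subjects in the Per-Protocol set. Endpoint 2 in the mITT Population is left without that protection. A woman who does poorly on study drug, is given something else and then has a negative culture is reported as an eradication for the drug she was randomized to.

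The error has a direction. The arm with more rescue gains more credited eradications, so a weaker drug can look closer to a stronger one than it is. No formal test is planned, so the reported proportions are themselves the efficacy result. It should be clear which treatment they describe.

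**Working it through.** **Step 1. The definitions side by side.** Take a subject whose baseline signs have resolved, who has no new sign, and whose TOC culture is negative.

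| Non-study antifungal before TOC | Clinical cure? | Mycological outcome | Overall success? |
|---|---|---|---|
| No | Yes | Eradication | Yes |
| Yes | No, barred | Eradication | No, cure is required |

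The antifungal changes the clinical and overall columns and leaves the mycological column as it was. If her signs had not resolved, she would be a clinical failure and the mycological entry would still be eradication.

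**Step 2. Inputs for size.** From Sample Size Determination: about 75 mITT subjects, 75% of those randomized evaluable, about 100 randomized. From Study Design: 1:1:1 allocation to three arms. The number given a non-study antifungal is not stated, so I assume k = 0 to 3 culture-negative rescued subjects per arm.

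**Step 3. The plan's own figure.** 75 / 0.75 = 100 randomized, which reproduces. With an even split, mITT subjects per arm = 75 / 3 = 25.

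**Step 4. Shift in one arm.** Shift = k / 25.

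| k | Points added to eradication |
|---|---|
| 0 | 0.0 |
| 1 | 4.0 |
| 2 | 8.0 |
| 3 | 12.0 |

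**Step 5. Shift in the difference between two arms.** The difference moves by (k1 − k2) / 25. Suppose 18 and 15 eradications without rescue in two arms (assumed counts):

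- Rescued cultures not counted: 18/25 − 15/25 = 72% − 60% = 12.0 points.
- Rescued negatives of 1 and 3 counted as eradications: 19/25 − 18/25 = 76% − 72% = 4.0 points.
- Rescued negatives of 0 and 3 counted: 18/25 − 18/25 = 0 points.

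Under these assumptions the observed difference narrows in the second case and disappears in the third.

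**Step 6. Scale against sampling error.** The 95% half-width for one arm is 1.96 × √(p(1 − p)/25): 19.2 points at p = 40% or 60%, and 17.6 points at 72%. For the difference 72% against 60% it is 1.96 × √(0.72 × 0.28/25 + 0.60 × 0.40/25) = 26 points.

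**The case against.** **Culture alone is a legitimate endpoint.** The mycological rule is explicit and gives every subject a category. Reporting the observed culture whatever else was taken is a choice that some trials make, and overall success already guards against credit for rescue. It is true that the definitions do not contradict each other and that endpoint 3 is protected. But endpoint 2 is reported separately and serves an objective about the drugs' own eradication rates, so protection of endpoint 3 does not repair it.

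**The indeterminate wording may cover her.** It speaks of a culture that cannot be interpreted. A valid negative culture can be read, and nothing says that a prior antifungal makes it uninterpretable. If that was the intention, two programmers could still code it differently.

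**The shifts are within noise and rest on invented counts.** This stands as a limit on importance. The half-widths in step 6 exceed every shift shown, and no rescue rate is given. The shift is nevertheless systematic, whereas sampling error is not.

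**Some rescued subjects may have cleared on study drug first.** This also stands, and it is the main cost of the change.

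**Stronger readings.** A reader might infer that clinical cure or overall success is inflated too. It is not, because both exclude these subjects. A reader might also infer that Per-Protocol membership cannot be derived at all. The supplied text does leave the phrase about an earlier therapeutic failure undefined: "Clinical outcomes will be assessed at the TOC Visit (Day 12) according to the following definitions", while "Vulvovaginal candidiasis signs and symptoms will be evaluated at screening and Days 1, 5, and 12", so Day 5 has scores but no response category. That matters only for otherwise eligible subjects given an active non-study antifungal before TOC. Lastly, a subject whose baseline signs resolved after such a drug, with no new sign related to vulvovaginal candidiasis or requiring antifungal treatment, fits none of the three clinical categories. In mITT this affects only the failure and indeterminate tabulation, not the cure or overall-success proportions. Both are minor wording points.

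**Conclusion.** The concern holds for endpoint 2. As written, a negative TOC culture after a non-study antifungal counts as eradication for the randomized drug, although the same subject is barred from clinical cure and overall success. The effect is 4.0 points per subject, given about 25 mITT subjects per arm in equal arms. It is 0 to 12 points per arm if 0 to 3 such subjects occur, and that count is an assumption. Unequal rescue can narrow or hide a difference between arms.

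The impact is limited: safety is the primary objective, efficacy is secondary and descriptive, and no sample size or test depends on the endpoint. The documents do not support a claim that the bias will be large, only that the rule permits it. The supplied text is a synopsis, so a fuller rule elsewhere cannot be excluded. The change is worthwhile because it is cheap, but the trial does not depend on it.

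**What to change.** For analysis only, with no change to who may receive another antifungal or when:

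1. In endpoint 2, count a subject who received a non-study antifungal before the TOC culture as not eradicated, and keep her in the denominator.
2. Use the same antifungal scope as the cure definition, that is, any further antifungal. The Per-Protocol criterion is narrower, covering only drugs with documented activity against the causative organism.
3. Give these subjects their own row in the mycological outcome table, by arm: *negative culture after non-study antifungal*. Without it they would have no category, since persistence needs a positive culture. The row also lets a reader recover the culture-only proportion by adding it back.

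The cost is one reworded definition and one table row. Cultures and concomitant medications are already to be recorded, and the number randomized stays at about 100. There are two drawbacks. The eradication proportion can only stay the same or fall compared with the present wording. A subject who had already cleared on study drug before taking the other antifungal would be counted as not eradicated.

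If the section is being edited anyway, define the earlier therapeutic failure in the Per-Protocol exception and say which clinical category the unlabelled subject takes. Neither is needed for the main change.
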